2. PLANNED ANALYSES

2.1. Interim Analysis

No interim analysis is planned for this study.

An Independent DSMB will be utilized in the study to ensure objective medical and/or statistical review of safety issues in order to protect the ethical and safety interests of subjects and to protect the scientific validity of the study. An external statistician will provide the required summaries to the DSMB. Further details of the DSMB review are described in the charter and separate DSMB SAP.

2.2. Final Analysis

Analysis of data in study URO-901-3006 includes baseline assessments and post-vibegron-exposure safety and efficacy data collected in study URO-901-3005 and depends on double-blind randomized treatment assignments from URO-901-3005. No treatment assignments from URO-901-3005 will be unblinded within study URO-901-3006 until after study URO-901-3005 has been formally unblinded.

eClinical Solutions, LLC will perform the production and quality control of all tables, figures and listings on behalf of Urovant Sciences, Inc.

Statistical programming will start after data have been collected and are available in the database. Blinded dry-runs using dummy treatment codes for study URO-901-3005 will be performed prior to database lock to ensure programming displays and algorithms are developed as planned.

The planned final analysis will be performed once the clinical database lock has taken place on both URO-901-3005 and URO-901-3006 and treatment codes for URO-901-3005 have been unblinded.

3. ANALYSIS POPULATION

3.1. Analysis Sets

3.1.1. All Subjects Extension

The All Subjects Extension consists of all subjects who signed the informed consent form (ICF) for URO-901-3006 and have screening data entered into the database. This population is used primarily for subject accounting purposes and will generally not be used for summary or analysis.

3.1.2. Safety Analysis Set Extension

The Safety Analysis Set Extension (SAF-Ext) will serve as the primary population for the analysis of safety data in this trial.

The SAF-Ext consists of all randomized subjects in Study URO-901-3005 who

- a) have completed the 24-week treatment period in the Study URO-901-3005, and
- b) enrolled into the extension Study URO-901-3006 and received at least one dose of vibegron in this study.

Safety endpoints will be descriptively summarized for the entire Safety Analysis Set Extension. No imputation will be performed for missing safety data. Baseline will be established as the last observation prior to the first dose of vibegron. All safety data collected on or after the first exposure to vibegron within the combined experience of the patient on URO-901-3005 and

URO-901-3006 will be included in the safety analysis for URO-901-3006, and all analyses by visit will index visits from the first dose of vibegron on either study; subjects who received placebo in study URO-901-3005 will only contribute safety data up to Week 28.

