1.1. Synopsis

Protocol Title: A Phase 3 Open-Label Extension Study to Evaluate the Long-Term Safety and Efficacy of Vibegron in Men with Overactive Bladder (OAB) Symptoms on Pharmacological Therapy for Benign Prostatic Hyperplasia (BPH)

Protocol Number: URO-901-3006

Brief Title: Extension Study of Vibegron in Men with OAB Symptoms With BPH

Study Rationale: Beta-3 adrenergic receptor (β_3 -AR) agonists have shown efficacy (with improved safety relative to anticholinergics) in treating persistent OAB symptoms in men on BPH therapies. This subset of the broader OAB population setting has unique safety needs (eg, possibility of urinary retention) that have not been fully evaluated in previous clinical programs of OAB treatments. Study URO-901-3006 is designed to evaluate long-term safety and efficacy of vibegron (75 mg once daily [QD] administered for 28 weeks) in men with symptoms of OAB while receiving pharmacological therapy for BPH who have received 24 weeks of study drug in double-blind, placebo-controlled, Phase 3 Study URO-901-3005.

Objectives: The primary study objective is to assess the long-term safety of vibegron when dosed for up to 52 weeks in men with OAB symptoms on pharmacological therapy for BPH who previously completed treatment in Study URO-901-3005. The primary clinical hypothesis is that vibegron + BPH pharmacological therapy for BPH treatment is safe for long-term use in men with OAB symptoms and BPH.

The secondary study objective is to assess the long-term efficacy of vibegron when dosed for up to 52 weeks in men with OAB symptoms on pharmacological therapy for BPH who previously completed treatment in Study URO-901-3005.

Endpoints:

Note: With respect to study endpoints, “per day” refers to a “Diary Day”, which is defined as the time between when the subject gets up for the day each morning and the time the subject gets up for the day the next morning as recorded in the subject bladder diary (approximately a 24-hour period).

Safety assessments will include treatment emergent AEs, clinical laboratory tests, physical examinations, vital signs, PVR volume, and Total IPSS.

Efficacy endpoints include the following:

- Change from baseline (CFB) at Week 52 in the average number of micturition episodes per day
- CFB at Week 52 in the average number of urgency episodes (urgency: need to urinate immediately) per day
- CFB at Week 52 in the average the number of nocturia episodes per night

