- CFB at Week 52 in the average number of urge urinary incontinence episodes per day in subjects with incontinence at baseline in Study URO-901-3005
- CFB at Week 52 in the average of International Prostate Symptom Score (IPSS) 1-week recall) Storage score (1-week recall)
- CFB at Week 52 in the average volume voided per micturition

See Section 3 (Objective and Endpoints) for the other/exploratory endpoints, including quality-of-life endpoints.

Statistical Methods:

Safety analyses will be based on all subjects who receive vibegron (through Week 52 of this extension study). Only one treatment group (vibegron) will be reported for safety data. Baseline will be the baseline for Study URO-901-3005. Descriptive statistics will be used to summarize safety endpoints.

The efficacy analyses will be for descriptive purposes only and will be conducted using the FAS-Extension population, which is a subset of the Study URO-901-3005 treated population which have completed the 24-week treatment period in Study URO-901-3005 and enrolled into this extension study.

The efficacy endpoints of change from baseline in average number of micturitions, average number of urgency episodes, average number of nocturia episodes, average number of urge urinary incontinence (UUI) episodes, average of IPSS storage score, and average volume voided per micturition will be analyzed separately using a mixed model for repeated measure (MMRM) with restricted maximum likelihood estimation. The analysis model for each efficacy endpoint will include terms or visit, baseline, baseline stratification factors (those found to be significant in Study URO-901-3005). An unstructured covariance matrix will be used to model the correlation among repeated measurements. The Kenward-Roger adjustment will be used with restricted (or residual) maximum likelihood (REML) to make statistical inference. The adjusted means for vibegron and visit will be estimated along with the 95% CI. Only the week-52 subjects (those on active treatment in Study URO-901-3005 and in Study URO-901-3006) will be included in the model.

Descriptive statistics will be used to summarize all efficacy endpoints. Summaries of efficacy endpoint will be presented by two treatment groups: vibegron for 52 weeks and vibegron for 28 weeks as determined by the randomized treatment in Study URO-901-3005.

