Vibegron is a potent and highly selective β 3-AR agonist demonstrating > 9000-fold selectivity for activation of β 3-AR over β 2-AR and β 1-AR in cell based in vitro assays. β -adrenergic receptors are prototypic G-protein coupled receptors expressed on the surface of cells, and mediate intracellular signaling via coupling to G_s and increasing levels of intracellular cyclic adenosine monophosphate (cAMP). β 3-ARs are widely distributed in humans and are the most prevalent β -AR subtype expressed on human detrusor smooth muscle [Takeda, 2000]. In isolated human bladder smooth muscle, activation of β 3-AR using subtype-selective agonists results in smooth muscle relaxation suggesting a role for β 3-AR agonists during the filling phase of the micturition cycle [Yamaguchi, 2002; Biers, 2006]. In rodent models of bladder overactivity, β 3-AR agonists relax bladder smooth muscle and suppress detrusor smooth muscle instability and hyperreflexia [Takeda, 2000; Woods, 2001; Takeda, 2002; Kaidoh, 2002]. In rhesus monkeys,

dose dependent increases in bladder capacity and decreases in micturition pressure were observed with vibegron. Bladder capacity was further increased by vibegron in combination with tolterodine or darifenacin [Di Salvo, 2017]. These results have supported a large and comprehensive clinical development program for vibegron in the general OAB population, including both male and female subjects.

More than 2300 subjects (including 1840 with OAB and 460 healthy volunteers) have received vibegron in Phase 1, 2, and 3 clinical studies. Assessment of safety laboratory parameters and mean vital sign values over time, including heart rate and blood pressure, showed no clinically meaningful differences for any active treatment group relative to placebo or anti-muscarinic comparators. A large, multicenter Phase 3 study of vibegron for the treatment of OAB in women and men is ongoing. Discontinuation rates due to adverse events (AEs) were low (< 5%) in all clinical studies conducted to date with vibegron. In a completed Phase 3 study in Japan in more than 1200 subjects with symptoms of OAB, there were no notable mean changes in post voided residuals observed [Yoshida, 2018]. A more detailed description of vibegron, including pharmacology, efficacy, and safety data in overactive bladder, is provided in the Investigator's Brochure.

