5.2. Exclusion Criteria

Subjects will not be eligible for inclusion in this study if any of the following criteria apply:

1. Experienced any SAE in Study URO-901-3005 that was reported as “possibly or probably related” to study treatment by the investigator.
2. Is a night-shift worker or plans to become a night-shift worker during the study.
3. Is using any prohibited medications as detailed in Section 10.6 (Appendix 7).
4. Is taking or using any medications to treat erectile dysfunction (ED) but is not using them on a regular schedule. If taking less than 2 times per week, ED medications with a short half-life such as sildenafil and vardenafil are allowed.
5. Has any planned procedures to treat ED (eg, implantation of a penile device) during the treatment period or has any planned prostate procedure.
6. Has a planned procedure to implant a sacral neurostimulation (SNS) or use of any posterior tibial nerve stimulation (PTNS) device.
7. Has coronary or neurovascular interventions planned during the duration of the study.

8. Has uncontrolled hyperglycemia (defined as fasting blood glucose > 150 mg/dL or 8.33 mmol/L and/or non-fasting blood glucose > 200 mg/dL or 11.1 mmol/L) based on most recent available lab results in Study URO-901-3005 or uncontrolled in the opinion of the investigator.
9. Has uncontrolled hypertension (systolic blood pressure of ≥ 180 mmHg and/or diastolic blood pressure of ≥ 100 mmHg) or has a resting heart rate (by pulse) > 100 beats per minute.
10. Has systolic blood pressures ≥ 160 mmHg but < 180 mmHg, unless deemed by the investigator as safe to proceed in this study and able to complete the study per protocol.
11. Subject has current evidence of any clinically significant condition, therapy, lab abnormality, or other circumstances that might, in the opinion of the investigator, confound the results of the study, interfere with the subject's ability to comply with study procedures, or make participation in the study not in the subject's best interest.

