8.4. Adverse Events and Serious Adverse Events

The definitions of an AE or SAE can be found in Section 10.3.

AEs will be reported by the subject (or, when appropriate, by a caregiver, surrogate, or the subject's legally authorized representative).

The investigator and any qualified designees are responsible for detecting, documenting, and recording events that meet the definition of an AE or SAE and remain responsible for following up AEs that are serious, considered related to the study drug or study procedures, or that caused the subject to discontinue the study drug or the study (see Section 7).

8.4.1. Time Period and Frequency for Collecting Adverse Event and Serious Adverse Event Information

All AEs and SAEs will be collected from the signing of the informed consent form through the end of study. In addition, any AEs and SAEs reported within 21 days after the last dose of study drug (5 half-lives of vibegron [half-life approximately 80 hours]) will also be collected. AEs will be collected at the timepoints specified in the Schedule of Assessments (Section 1.3), and as observed or reported spontaneously by study subjects.

Medical occurrences that begin before the start of study drug, but after obtaining informed consent will be recorded in the AE section of the eCRF.

All SAEs (including serious AESIs) will be recorded and reported on the eCRF within **24 hours** of the study site personnel's knowledge of the event, as indicated in Section 8.4.4. Marking the event as "serious" will automatically send required notifications for Sponsor or designee review. The investigator will also submit any updated SAE data within 24 hours of receipt of the information. Nonserious AESIs will be reported on the eCRF within **72 hours** of the site's knowledge of the information

Investigators are not obligated to actively seek AE or SAE information after conclusion of the study participation. However, if the investigator learns of any SAE, including a death, at any time after a subject has been discharged from the study, and he/she considers the event to be reasonably related to the study drug or study participation, the investigator must promptly notify the Sponsor or designee.

The method of recording, evaluating, and assessing causality of AEs and SAEs and the procedures for completing and transmitting SAE reports are provided in Section 10.3.

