9.1. Hypotheses

9.1.1 Primary Objective and Hypothesis

The primary study objective is to demonstrate long-term safety of vibegron 75 mg in men with BPH with symptoms of OAB. There is no formal statistical primary endpoint hypothesis. Descriptive statistics will be used to evaluate safety endpoints, including the incidence of treatment-emergent AEs (SOC and PT) by originally randomized treatment group and for vibegron treatment overall, including events during all vibegron exposure from both Study URO-901-3005 and URO-301-3006.

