9.3.2. Safety Analysis Populations

The Safety Analysis Set - Extension (SAF-Ext) population will be used to for the analysis of safety data in this study.

The SAF-Ext consists of all randomized subjects in Study URO-901-3005 who

- a) have completed the 24-week treatment period in the Study URO-901-3005, and
- b) enrolled into the extension Study URO-901-3006 and received at least one dose of vibegron in this study.

The SAF-Ext will be used for all the safety analyses. Safety endpoints will be descriptively summarized based on the treatment in study URO-901-3006. This means there will be one vibegron treatment group (combining 52 weeks of vibegron dosing for those continuing vibegron from Study URO-901-3005 and 28 weeks of vibegron dosing for those who received placebo in Study URO-901-3005).

No imputation will be performed for missing safety data. Baseline will be the same as the baseline defined in the parent study. Further inclusion of data from URO-901-3005 in the reporting of this study will be described in the SAP.

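### The extension safety set requires 24 completed parent-study weeks but counts events and exposure from first vibegron dose, so the 52-week and overall figures for deaths, AE discontinuations and related SAEs mainly reflect Weeks 24-52; the treatment-emergent window also ends 16 days earlier in the SAP than in the protocol

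*SAP*

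**What the plan says.** **Who is in the set.** Protocol 9.3.2 and SAP 3.1.2 define the same extension safety set: men randomized in the parent study who completed its 24-week treatment period, enrolled in the extension and took at least one vibegron dose there. This fits the objective in the synopsis, which is limited to men "who previously completed treatment in Study URO-901-3005". Protocol 5.2, criterion 1, also bars anyone who "Experienced any SAE in Study URO-901-3005 that was reported as" possibly or probably related. SAP 7.3 uses the same two categories to define a treatment-related event.

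**What is counted.** SAP 3.1.2 takes in "All safety data collected on or after the first exposure to vibegron within the combined experience of the patient" across both studies. SAP 7.1 (exposure), Table 2 and SAP 7.3 (TEAEs) use the same starting point. SAP 4.2.1 and 4.2.2 present safety in 52-week, 28-week and overall columns. Fatal TEAEs, TEAEs leading to discontinuation, treatment-related serious TEAEs and AESIs each have a planned table on this set.

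**What the protocol asks for.** The synopsis says "Safety analyses will be based on all subjects who receive vibegron (through Week 52 of this extension study". Protocol 9.1.1 asks for TEAE incidence by original arm and "for vibegron treatment overall, including events during all vibegron exposure from both Study URO-901-3005 and URO-301-3006". Protocol 9.4.2 starts the treatment-emergent period at first dose in this study. It ends the period 21 days after last dose, or at another investigational agent or surgical intervention if that comes first. Protocol 9.3.2 adds: "Further inclusion of data from URO-901-3005 in the reporting of this study will be described in the SAP".

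**Where the SAP ends the window.** SAP 7.3 ends it 5 days after last dose. Table 2 ends it at 5 days or the end-of-study visit, whichever is earlier. Section 9 of the SAP lists neither.

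**The concern.** Membership depends on what happened up to Week 24, but the clock starts at Week 0. A man randomized to vibegron who died, or who stopped drug for an AE, before Week 24 is not in the set. One with a related SAE in the parent study should not be. For these outcomes the first 24 weeks of the 52-week column are close to event-free by construction. The 28-week column does not have this feature, because its first vibegron dose is the first extension dose. A reader who sets the two columns side by side may take them as 52 and 28 weeks of the same risk.

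Long-term safety is the primary objective and all safety analysis is descriptive, so these displayed percentages are the primary result.

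The end of the window raises a separate matter. The protocol collects "any AEs and SAEs reported within 21 days after the last dose of study drug", but the SAP's TEAE tables stop at 5 days or sooner.

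**Working it through.** **1. The plan's own figure.** Protocol 9.7 and SAP 1.2.4 give about 300 men, about 33% dropout and 100 completing one year on vibegron. With an assumed 1:1 split (the documents give no ratio), 150 × 0.67 = 100.5, which reproduces the 100. Conversely, 100/0.67 = 149 vibegron men rolled over.

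**2. Share of follow-up that is near event-free.** In the 52-week column this is 24/52 = 46%. In the overall column at 1:1 it is (150 × 24)/(150 × 52 + 150 × 28) = 3600/12000 = 30%.

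**3. Which categories.**
- Deaths and AE discontinuations completed in Weeks 0-24: none possible. An AE that starts then but leads to stopping in the extension still counts, because TEAEs are placed by start date (Table 2).
- Treatment-related SAEs: near zero, not zero. Causality may be revised later (protocol 10.3), and a missing relationship is set to probably related (SAP 4.2.3).
- Urinary retention and PVR ≥ 300 mL: probably the same. Protocol 2.4.2 states the withdrawal rule directly after the parent study's entry criteria. Whether the parent study applied that rule is not shown.
- Clinically significant laboratory abnormalities at Week 24: these bar entry (protocol 8.3.4).

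**4. Illustrative size.** The documents give no event rates by duration. The nearest statement is "Discontinuation rates due to adverse events (AEs) were low (< 5%) in all clinical studies conducted to date with vibegron". I therefore assume a true net 52-week risk r of 1%, 2% or 5%, with cumulative hazard H = −ln(1 − r) and a share f of H falling before Week 24.

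- 52-week column = 1 − exp(−(1 − f)H)
- 28-week column = 1 − exp(−(f + (4/28)(1 − f))H)

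| f | 52-week column at r = 1/2/5% | 28-week column |
|---|---|---|
| 24/52 (constant hazard) | 0.54 / 1.08 / 2.72% | 0.54 / 1.08 / 2.72% |
| 0.60 | 0.40 / 0.80 / 2.03% | 0.66 / 1.32 / 3.31% |
| 0.25 | 0.75 / 1.50 / 3.77% | 0.36 / 0.72 / 1.82% |

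This assumes no other dropout. Under constant hazard the ratio of the 52-week column to r is 0.54 (0.540 to 0.545). The overall column at 1:1 is then about 0.70 of the net value.

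**5. With the stated 33% dropout, spread over the extension.** The dropout hazard is λ = −ln(0.67)/28 = 0.0143 per week. Mean extension follow-up is 0.33/λ = 23.07 weeks. With h = H/52, expected events in 149 men are 149 × h/(h + λ) × (1 − exp(−28(h + λ))) = 0.66, 1.33 and 3.35 at r = 1, 2 and 5%. Exposure-adjusting the same set from first dose gives 23.07/(24 + 23.07) = 0.49 of the true rate, so adjustment within this set does not cure the problem.

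**6. Direction.** The comparator above is net risk from first dose. A crude percentage among all starters mixes follow-up lengths. If a proportion p of starters rolls over and other losses occur at Week 24, it equals e + p(1 − e)L, where e is early risk and L is late risk. With f = 0.10, p = 0.67 and r = 5%, e = 0.51% and L = 4.51%, giving 3.52%. That is below the 4.51% shown in the extension set.

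**7. Window end.** The SAP window is 21 − 5 = 16 days shorter. Protocol 8.4.1 gives a half-life of about 80 hours. Five days is 120/80 = 1.5 half-lives (2^−1.5 = 35% remaining under first-order decline). Twenty-one days is 504/80 = 6.3 half-lives (1.3%).

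**The case against.** The safety set is the one the protocol defines and it matches the objective, so a reader who infers that the wrong population was chosen goes too far. The synopsis wording about all subjects who receive vibegron reads naturally as extension subjects. Every safety table is labelled with the set, and the table shells, where footnotes would sit, are not shown. Early events in all starters belong first to the placebo-controlled parent study. All of this stands. It supports keeping the set. It does not tell the reader of the 52-week column what that column is conditional on.

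A reader might also infer that the SAP moved the start of the treatment-emergent period without authority. The documents do not support that. Protocol 9.1.1 asks for events during all vibegron exposure from both studies, and 9.3.2 leaves use of parent data to the SAP. The conflict is inside the protocol, between 9.1.1 and 9.4.2.

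Nor are events on days 6-21 lost: SAP 7.3 lists all AEs for the safety set, treatment-emergent or not. They leave the TEAE tables, not the report.

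**Conclusion.** The point holds, with limits. The mechanism follows from the documents alone: the fatal, AE-discontinuation and treatment-related serious categories in the 52-week and overall columns mainly reflect Weeks 24-52, and urinary retention probably does too. The SAP text plans no caveat. The size is illustrative. The figure of about 0.54 of net 52-week risk rests on constant hazard and no other dropout; the overall figure and the event counts in 149 men also rest on an assumed 1:1 split. If little of the risk falls before Week 24, the effect is small.

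Two stronger readings fail. The percentages do not understate every possible comparator, because a crude all-starter percentage can be lower. And it cannot be said that only three categories are touched, given the retention rule and the Week 24 laboratory exclusion.

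The difference at the end of the window (21 days against 5 days, or the end-of-study visit if earlier) needs no assumption. Neither it nor the dropped cut-off at another agent or surgery is recorded in SAP Section 9. Both matters should be fixed before the final analysis.

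**What to change.** 1. Footnote the 52-week and overall columns of the fatal, discontinuation, treatment-related serious and AESI tables (urinary retention at least): figures are conditional on completing 24 parent-study weeks and entering the extension. Point to the parent-study report for Weeks 0-24 in all vibegron starters.
2. Add a small supplementary summary of these categories for every subject with at least one vibegron dose in either study, using exposure-adjusted rates or time-to-event estimates from first dose. Avoid crude percentages there.
3. Align the end of the treatment-emergent period in SAP Table 2 and SAP 7.3 with the protocol's 21-day analysis and collection window, or add a 21-day sensitivity table. Reconcile the end-of-study limit, the dropped cut-off at another agent or surgery, and protocol 9.1.1 with 9.4.2 on the start. Record each choice and its reason in SAP Section 9.

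**Cost.** Footnotes, one or two tables and a Section 9 entry. SAP 2.2 already makes the final analysis wait for both database locks and parent-study unblinding, so no new data are collected. The real work is in item 2: parent-study men who did not roll over must be added to the analysis datasets, and the parent study's TEAE window must be checked for comparability.
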